We will assess this hypothesis in the context of a two factor repeated measures mixed model ANOVA, with one between subjects factor with two levels (pregnenolone vs. placebo) and one within subjects factor with three levels (Weeks 0, 4, 8 of treatment post-randomization, which correspond to Visits 2, 4, and 6). This hypothesis will be tested using the treatment-by-time interaction, followed by contrasts in least squares means. These contrasts will examine the difference between the treatments at Weeks 4 and 8 on the changes between least squares means between Week 0 to Week 4, and Week 0 to Week 8 of treatment post-randomization. We will perform several such analyses, one for functional outcome as assessed by the Physical Component of the SF-36 (primary endpoint), and others for secondary endpoints, including: pain symptoms (as assessed by the Brief Pain Inventory), executive functioning (as assessed by the Tower of London test of the BACS), fatigue (as assessed by the Multidimensional Fatigue Inventory), and overall psychological functioning (as assessed by the Global Severity Index of the SCL-90R). The response variable will be change from baseline, and we will use baseline as a covariate. Exploratory outcomes will include the BACS composite score (cognitive symptoms), resilience (as assessed by the Connor-Davidson Resilience Scale), anxiety and depression symptoms (as assessed by the Hospital Anxiety and Depression Scale), PTSD symptoms (as assessed by the PTSD Symptom Checklist), and depression symptoms (as assessed by the Beck Depression Inventory-II scale).

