8. At Visit 6 (=8 weeks post-randomization), the study medication will be tapered (150 mg BID x 2 days, followed by 50 mg BID x 2 days, followed by study medication discontinuation). Subjects will return 1-2 weeks after Visit 6 for a follow-up visit that includes vital signs, laboratory tests, administration of the CSSRS to assess for suicidality, and adverse event assessment.

9. The WRAT, HADS, and TBI screen will be administered at Visit #1. The SF-36, BAC-A, BPI, MFI, SCL-90, HADS, BDI, PCL, WHODAS, SDS, and CDRS will be administered at Visits #2, 4 and 6. The Adverse Event Scale and CSSR (to assess for suicidality) will be administered at each in-person visit and at each telephone visit.

Randomization and Maintenance of the Blind: Randomization will occur in blocks of 10, and will be conducted by the research pharmacist at the Durham VAMC. Only the research pharmacist will have access to the randomization code during conduction of the study, and the PI and all raters, investigators and other study staff will be blinded during the study. The pharmacist does not participate in assessing any of the primary symptom or side effect dependent variables, and conveys no information about treatment assignment to subjects or staff. Study medication will be dispensed every two weeks. Subjects will be given six extra days of medication in case of a delayed or rescheduled appointment. The blind will be broken only if a medical emergency requires this information. If this occurs, the subject will be withdrawn from the study.

After the study is completed and the last participant leaves the study, the aggregate blinded data will be cleaned (i.e. reviewed for possible outliers that may reflect data entry errors, etc.) and the database will be locked. A de-identified copy of the locked data will be given to our PhD-level statistician for analysis. A de-identified copy of the locked data will also be give to a second statistician for independent replication of the study analyses. The PI will not be involved in study data analyses.

Neurosteroid Quantification:

Gas Chromatography/Mass Spectrometry (GC/MS) Preceded by High Performance Liquid Chromatography (HPLC)

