Preliminary Exploration: We will explore the data using descriptive statistics and graphical techniques prior to any hypothesis testing. For categorical variables, we will examine frequency distributions and where appropriate contingency tables and histograms. For continuous variables, we will examine frequency distributions and where appropriate stem-and-leaf plots and box-and-whisker plots. When appropriate, we will consider transformation. If

necessary, due to distributional considerations, we will consider a change of analysis method to a less parametric one. For time-to-event variables, we will use Kaplan-Meier plots to obtain a global picture of the patterns in each of the treatment groups.

General Modeling: Most of our hypotheses specify continuous response variables assessed longitudinally. For those models, we will use mixed models repeated measures models. There are three assessment points for the primary and secondary outcome measures (to be administered at Visits 2, 4, and 6; each study visit is two weeks apart). We will use an AR(1) covariance structure for the repeated measures. We will fit the models preliminarily using AR(1) covariance structures and using unstructured covariance structures, and use the difference between the two -2 log likelihood functions to construct a likelihood ratio test of the advantage of the unstructured covariance structure. If the unstructured covariance structure does not fit significantly better, we will use an AR(1) structure.

We will examine group differences in least squares means at each of the major time points (Weeks 0, 4, 8 of treatment post-randomization) as described in the plans for specific hypotheses. Distributional assumptions will be examined using residuals. We recognize that it is always possible that these mixed models may fail to converge or encounter difficulties based on their use of asymptotics. In that case, we will move to analyses that assume compound symmetry, and use a Huynh-Feldt correction for the extent to which compound symmetry fails to be met.

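### Response variable and time factor conflict in the primary model: the planned covariance test cannot be computed, and the fallback trigger is unclear when only the unstructured fit fails

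*Combined protocol and SAP*

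**What the plan says.** Study Interventions, under the primary outcome hypothesis, describes a repeated measures mixed model with a two-level treatment factor and "one within subjects factor with three levels (Weeks 0, 4, 8 of treatment post-randomization, which correspond to Visits 2, 4, and 6"). The hypothesis is tested by the treatment-by-time interaction and then by contrasts: "These contrasts will examine the difference between the treatments at Weeks 4 and 8 on the changes between least squares means", from Week 0 to Week 4 and from Week 0 to Week 8. The same paragraph adds: "The response variable will be change from baseline, and we will use baseline as a covariate". It applies this model to the secondary endpoints as well.

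Study Timeline, item 9, fixes the assessments: "The SF-36, BAC-A, BPI, MFI, SCL-90, HADS, BDI, PCL, WHODAS, SDS, and CDRS will be administered at Visits #2, 4 and 6". The only SF-36 score that can serve as baseline is therefore the Visit 2 score, which is Week 0.

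The Statistical Analysis Plan, General Modeling, again lists Weeks 0, 4 and 8 as the time points. It makes AR(1) the default covariance, fits AR(1) and unstructured models, and will "use the difference between the two -2 log likelihood functions to construct a likelihood ratio test of the advantage of the unstructured covariance structure". The rule after that test reads: "If the unstructured covariance structure does not fit significantly better, we will use an AR(1) structure". The section also has a fallback. Its trigger is worded as follows: "We recognize that it is always possible that these mixed models may fail to converge or encounter difficulties based on their use of asymptotics". The action attached to that trigger is: "In that case, we will move to analyses that assume compound symmetry, and use a Huynh-Feldt correction".

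**The concern.** A Week 0 level belongs with raw scores, where the interaction and the Week 0 contrasts have their usual meaning. Change from baseline with baseline as covariate belongs with post-baseline visits only. Combined as written, they give a Week 0 response that is a constant.

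Two things follow. A step that the plan requires, the covariance test, cannot be carried out. And the plan's decision rule then has a gap: AR(1) fits, unstructured does not, and the text covers neither outcome explicitly. This is the confirmatory test of the primary endpoint. The plan promises an analysis fixed in advance and repeated by a second statistician, so both should be able to derive the same model from the text.

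**Working it through.** **The plan's own figure.** The Power Analysis for the SF-36 uses a two-sided two-sample t-test with 70 per group, difference 7, SD 12.5 and alpha 0.05. The noncentrality is (7/12.5) × √(70/2) = 0.56 × 5.916 = 3.313 on 138 df, with critical value 1.977. Power is 0.908, matching the printed 0.90822. This is a t-test figure and does not depend on the model discussed here.

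**Week 0 under the stated response.** Change at Week 0 = (Visit 2 score) − (Visit 2 score) = 0 for every participant. Its variance is 0, and the 3×3 covariance matrix of change at Weeks 0, 4 and 8 has rank 2.

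**Unstructured fit.** Let v be the Week 0 variance and n the number of participants. The Week 0 part of −2 log L is n·ln(v) + Σ(residual²)/v. With Week 0 means and baseline slope at zero, every Week 0 residual is zero, the second term vanishes, and n·ln(v) goes to minus infinity as v goes to 0. With n = 140, each 100-fold cut in v lowers −2 log L by 140 × ln(100) = 644.7. Numerically:

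| v | −2 log L |
|---|---|
| 1 | 2394.5 |
| 10⁻² | 1749.8 |
| 10⁻⁴ | 1105.1 |
| 10⁻⁸ | −184.4 |

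There is no finite minimum, so the difference in −2 log L from AR(1) is not defined.

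**AR(1) fit.** This stays finite (about 2938 by REML in one simulated data set), because one variance is shared by all three weeks and Weeks 4 and 8 do vary. The price is that a constant Week 0 is given the same residual variance as the other two.

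**Size of the effect.** Assumptions: SD 12.5 from the power section; visit correlation 0.5 or 0.7, constant or decaying with time (0.5 appears in the document only for the Tower of London); dropout completely at random. Week 0 is kept, with one common baseline slope, REML, and tests at nominal 5%. The 30 per arm comes from Subject Recruitment: 140/(1 − 0.30) = 200 randomized, and (200 − 140)/2 = 30 per arm not reaching Visit 4. That their Week 0 rows enter the model is an assumption.

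| Interaction test, no true effect | Rejection rate |
|---|---|
| AR(1), 70 per arm complete | 5.5–6.5% (7,000 trials per cell); smaller runs up to 7.1% |
| AR(1), plus 15 per arm with Week 0 only | 6.9–7.9% |
| AR(1), plus 30 per arm with Week 0 only | 8.5–9.2%; smaller runs up to 9.3% |
| Classical Huynh-Feldt on completers | 4.4–5.3% |

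Monte Carlo standard error is 0.3–0.4 points for the 7,000-trial runs. Week-0-only participants raise the rate because they add near-zero residuals, which shrink the pooled variance, and carry no information on change.

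**Do the two named routes agree?** At the plan's 7 points held at both visits, with complete data, AR(1) and Huynh-Feldt gave different decisions at the 5% level in 0.3–9.0% of trials when Huynh-Feldt included baseline, and in 0.2–3.3% when it did not. AR(1) interaction power at that effect was 89–99%.

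**The case against.** The strongest reply is that the plan already sets an order. AR(1) is the default. Unstructured replaces it only if it fits significantly better, and a fit with no valid statistic has not shown that. On this reading AR(1) stands, it converges, and it tests the interaction and contrasts that Study Interventions names. With complete data its Week 0-to-8 contrast equals the unadjusted difference in mean change, which is a sensible estimate.

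Most of this stands. A reader might infer that the plan leaves the primary test without any route; it does not, since a default and a fallback are both named. What remains open is narrower. The fallback is triggered when the mixed models fail to converge or meet difficulties, and an unbounded unstructured fit can fairly be read as that. The text does not say whether that failure alone moves the analysis to compound symmetry or leaves AR(1) in place.

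Three other strong readings are also not supported:

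- **Frequent opposite verdicts.** At an assumed 4-point benefit, AR(1) and Huynh-Feldt with baseline disagree in roughly 12–22% of complete-data trials. But 4 points is not in the document. Huynh-Feldt with and without baseline differ in 11–23% of such trials, and the two valid repairs proposed below (with the joint test for the first) differ in 12–25%. Without baseline the gap from AR(1) is 3–8%. The larger figure mainly reflects baseline adjustment.
- **A lost covariate.** With complete data and a common slope, baseline cancels from the Week 0 contrasts. That costs precision, not validity.
- **Collapsed power.** If Week 0 were dropped and the interaction kept, the test would ask only whether the effect differs between Weeks 4 and 8, with power near 5% for a constant 7 points at correlation 0.5. The plan does not say this, and its Week 0 contrasts contradict it.

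**Conclusion.** The contradiction is real and follows from the text alone: response, time factor and assessment schedule together make Week 0 a constant, and the planned covariance test then has no finite value. The rule for what happens next is incomplete when only the unstructured fit fails.

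The consequence is moderate. Under the assumptions listed, the literal AR(1) interaction test runs at about 5.5–7% with 70 complete per arm. A reader might infer serious error inflation. That needs about 30 Week-0-only participants per arm kept in the model (about 8.5–9%), which the plan neither states nor excludes. At 7 points the two named routes disagree in about 0–9% of complete-data trials. The stated 90% power is not in question. This should be corrected before unblinding, but it does not invalidate the primary comparison.

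**What to change.** Make the response and the time factor agree in Study Interventions and in General Modeling, and state one model for the primary and secondary endpoints. Either:

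- **(a)** Response is change at Weeks 4 and 8 only. Fixed effects are treatment, week, treatment-by-week, baseline and baseline-by-week, with an unstructured 2×2 covariance. A named treatment least-squares-mean contrast, or a joint 2-df test of both weeks, replaces the interaction as the primary test.
- **(b)** Response is the raw score at Weeks 0, 4 and 8, with the treatment-by-time interaction and the contrasts already planned. Delete the sentence on change from baseline and the baseline covariate.

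In either case, say exactly what triggers the compound-symmetry/Huynh-Feldt fallback, and whether participants with only a Week 0 assessment enter the model. In simulation on completers, both options held 4.5–5.4% error.

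The cost is wording only, with no extra data or participants. Option (b) gives up the precision of baseline adjustment: the contrast variance is 2σ²(1 − r) against σ²(1 − r²), a ratio of 2/(1 + r), where r is the baseline-to-Week 8 correlation. That is 1.18 at r = 0.7 and 1.60 at r = 0.25 (correlation 0.5 decaying over two steps). Under option (a), if Week 8 alone is decisive, recheck the stated power, because Subject Recruitment counts its 140 participants at Week 4 and gives no Week 8 number.

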For the purpose of power calculations we assume that the mean pain levels of the two independent groups will be compared using a Two-Sample T-Test, Null Hypothesis: Mean1=Mean2. Alternative Hypothesis: Mean1 > Mean2. The standard deviations were assumed to be unknown and equal.

Assuming specified numbers of participants in each group (N) the mean differences detectable for at least 80% power and alpha=0.05 are shown in the following table and figure.

N1	Mean1	Mean2
4	6.0	3.6
5	6.0	3.8
6	6.0	4.0
6	6.0	4.2
8	6.0	4.4
10	6.0	4.6
12	6.0	4.8
17	6.0	5.0
26	6.0	5.2
45	6.0	5.4
100	6.0	5.6

Group sample sizes of 45 achieve at least 80% power to detect a difference of 0.6 between the null hypothesis that both group means are 6.0 and the alternative hypothesis that the mean of group 2 is 5.4 with estimated group standard deviations of 1.0 and 1.0 and with a significance level (alpha) of 0.05 using a two-sided two-sample t-test. We will have 70 Veterans per group, and should thus have **94% power to detect a difference in pain symptoms of 0.6** in the pregnenolone intervention compared to placebo.

POWER ANALYSIS: COGNITIVE SYMPTOMS (Secondary Endpoint)

Executive functioning as assessed by the Tower of London Test of the BACS cognitive assessment battery, Keefe et al.

The Tower of London component of the BACS cognitive assessment battery demonstrated improvements in the hypothesized direction in two of our prior pilot RCTs in Veterans with schizophrenia and mild TBI who had been randomized to pregnenolone (moderate effect sizes). We thus did power and sample size calculations for Tower of London executive functioning scores (secondary cognitive outcome measure) from estimates of means and standard deviations (SD) from preliminary data derived from our pilot RCT examining pregnenolone in OEF/OIF era Veterans with mild TBI. We conservatively utilized our pilot RCT in Veterans with TBI rather than our pilot RCT in Veterans with schizophrenia, as Veterans with schizophrenia demonstrated somewhat greater mean improvements in the Tower of London test (z-score change 0.61 greater than placebo). We used simplified models on change scores for power calculations as we do not know, and cannot reasonably estimate, the covariance parameters we would need to do these calculations in the context of the mixed models. We used correlations of 0.50 between all occasions, which is probably a conservative estimate (please see attached scoring information for BACS in Appendix).

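### As written, the primary model's single baseline slope cancels from the primary contrasts; the responses should be the Week 4 and Week 8 changes, with a baseline-by-visit term

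*Combined protocol and SAP*

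**What the plan says.** The primary analysis is described under STUDY INTERVENTIONS, Primary Outcome. It is a repeated measures mixed model with treatment as the between-subjects factor and "one within subjects factor with three levels (Weeks 0, 4, 8 of treatment post-randomization, which correspond to Visits 2, 4, and 6". On the test: "This hypothesis will be tested using the treatment-by-time interaction, followed by contrasts in least squares means". The contrasts compare the arms on the change in least squares means from Week 0 to Week 4 and from Week 0 to Week 8. On the response and covariate: "The response variable will be change from baseline, and we will use baseline as a covariate".

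General Modeling in the Statistical Analysis Plan again lists Weeks 0, 4 and 8 as the time points for least squares means. It sets the covariance default, "We will use an AR(1) covariance structure for the repeated measures", and the selection rule, "If the unstructured covariance structure does not fit significantly better, we will use an AR(1) structure". Neither section names a baseline-by-visit term.

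Study Timeline, item 9, gives the SF-36 at Visits 2, 4 and 6, so there is one score before randomisation.

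**The concern.** The elements of the model do not fit together. If the response is change from baseline, its value at Week 0 is zero for every participant, yet Week 0 is a level of the time factor and the reference point of both contrasts. Baseline is named only as a covariate, which in ordinary usage is a main effect with one slope. A term that shifts all of a participant's time points by the same amount cannot affect a comparison between time points, and every primary comparison is of that kind.

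Precision is at stake. Adjusting for baseline costs nothing and is evidently intended. A programmer who follows the text literally would get an unadjusted change-score comparison. One who drops Week 0 would get an adjusted comparison. The two can differ materially in variance, and the text does not say which is meant.

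**Working it through.** **Inputs from the documents.** 70 per arm, difference 7 points (33.7 against 40.7), SD 12.5 in each arm, two-sided alpha 0.05 (Power Analysis, Physical Component of the SF-36).

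**Assumed.** The correlation between SF-36 scores at different visits, which is not given. Let c be the correlation between Week 0 and Week 8. Under AR(1) on the raw scores with rho per four-week step, c = rho². The only correlation in the documents, "We used correlations of 0.50 between all occasions", is in the Tower of London power calculation; I use 0.50 as an illustration. Data are complete; dropout is not modelled.

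**Step 1. Reproduce the stated power.** A noncentral two-sample t calculation gives 0.90822, as in the protocol's table. It uses the full SD, a variance factor of 1, so it takes no credit for baseline adjustment.

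**Step 2. The cancellation.** In the literal model the mean for arm g at time t is m(g,t) + b × (baseline − mean baseline). The Week 8 minus Week 0 difference within an arm is m(g,8) − m(g,0); b appears at both times and drops out. With complete data and a separate mean for each arm and time, the estimated contrast is the raw difference in mean change. I fitted this model by generalised least squares to one simulated data set of 140. The estimated slope was −0.40, but the Week 0-to-8 contrast equalled the raw difference in mean change, apart from rounding error.

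**Step 3. Variance at Week 8, in units of SD².**

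- Literal model (unadjusted change): 2(1 − c).
- Week 8 change with its own baseline slope: 1 − c².
- Ratio: 2(1 − c)/(1 − c²) = 2/(1 + c).

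| Assumed correlation | c | Literal | Own slope | Ratio | Power, literal | Power, own slope |
|---|---|---|---|---|---|---|
| AR(1), rho 0.3 | 0.09 | 1.82 | 0.9919 | 1.83 | 0.684 | 0.910 |
| AR(1), rho 0.5 | 0.25 | 1.50 | 0.9375 | 1.60 | 0.766 | 0.925 |
| AR(1), rho 0.7 | 0.49 | 1.02 | 0.7599 | 1.34 | 0.903 | 0.965 |
| AR(1), rho 0.9 | 0.81 | 0.38 | 0.3439 | 1.10 | >0.999 | >0.999 |
| Equal, 0.50 | 0.50 | 1.00 | 0.75 | 1.33 | 0.908 | 0.967 |

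A 20,000-run simulation with 70 per arm gave ratios of 1.57 at rho 0.5 and 1.34 at rho 0.7. The literal variance exceeds the planning value of 1 whenever c is below 0.5.

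**Step 4. The milder reading: responses at Weeks 4 and 8 only, one slope.** If AR(1) holds for the raw scores, the raw-score slope on baseline is rho at Week 4 and rho² at Week 8. A common slope b gives Week 8 variance 1 − 2bc + b². At rho 0.5:

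- Equal weighting of visits: b = (0.5 + 0.25)/2 = 0.375. Variance = 1 − 0.1875 + 0.1406 = 0.953, which is 1.7% above 0.9375.
- Generalised least squares weighting: b = rho/(1 + (1 − rho)²) = 0.5/1.25 = 0.4. Variance = 1 − 0.20 + 0.16 = 0.960, which is 2.4% above.

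Over rho 0.3 to 0.9 the cost is 0.6-1.7% with the first b and 1.2-3.1% with the second. The power loss is below 0.6 percentage points at 7 points. Under equal correlations the slopes coincide and the cost is zero.

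**The case against.** The best defence is that no experienced statistician would fit the literal model. A response that is always zero at Week 0 would be noticed, the record dropped, and the Week 4 and Week 8 changes analysed with baseline adjustment. The loss is then at most about 3%, and power stays above the planned level for most correlations in Step 4. This is fair as a forecast of practice. It does not settle the text, which lists Week 0 as a level and defines both contrasts from it. The plan is meant to be fixed in advance and replicated by a second statistician, so it should not depend on a silent repair.

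Some stronger readings are tempting, and the documents do not support them.

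- *That the plan commits to one slope.* It does not say so; this is the natural reading of a covariate named alone.
- *That the slopes must differ under the AR(1) default.* This follows only if AR(1) describes the raw scores at Weeks 0, 4 and 8. AR(1) on the Week 4 and Week 8 residuals after baseline adjustment says nothing about the slopes, and the plan may switch to an unstructured covariance.
- *That the stated 90% power is lost.* On the literal reading it falls short only when c is below 0.5 and the SD is near 12.5. With the SD of 7.5 that the protocol cites from a prior study, literal power at rho 0.5 is 0.994.
- *That an SF-36 at Visit 1 was overlooked.* A reader may note "The WRAT, HADS, and TBI screen will be administered at Visit #1" and that HADS is repeated at Visit 2, and infer that a second baseline score would add precision. Under the AR(1) default the Visit 1 score has coefficient zero once Visit 2 is in the model, so the gain is nil. At equal correlation 0.50 it would cut variance by 11.1% (0.750 to 0.667), but that pattern is undocumented for the SF-36, and Visit 1 precedes the placebo lead-in. A single baseline after the lead-in is a coherent design, not an error.

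**Conclusion.** The point holds as one of model specification. On the literal reading the baseline covariate does no work in the primary test, and Week 8 variance is 2/(1 + c) times what visit-specific adjustment would give: 1.60 times under AR(1) with rho 0.5, and 1.33 times at equal correlation 0.50. On the Weeks 4-and-8 reading the loss is about 1-3% if AR(1) describes the raw scores, and nil under equal correlations.

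These sizes rest on assumed correlations, equal SDs across visits, complete data and 70 per arm. The cancellation itself needs no assumed correlation, only complete data and a separate mean for each arm and time. Treatment comparisons remain valid under randomisation on either reading; what is lost is precision and a clear definition of the primary test. This is a low-cost improvement, not a threat to the trial.

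**What to change.** In the Primary Outcome section:

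- State that the responses are the changes from Week 0 to Week 4 and from Week 0 to Week 8, and remove Week 0 as a level of the time factor.
- Specify the fixed effects as treatment, visit, treatment-by-visit, baseline and baseline-by-visit.
- Define the primary test as the treatment difference in adjusted mean change at those visits. This must change together with the time factor: with two visits left, the treatment-by-visit interaction tests only whether the effect differs between Week 4 and Week 8.

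Amend General Modeling to match, so that least squares means are compared at Weeks 4 and 8 and the covariance structure applies to those two residuals. The same wording would serve the secondary endpoints, which share the model.

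The cost is one extra model parameter per endpoint and an edit made before database lock. No new data or change to the visit schedule is needed.
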